12.1 Appendix 1: Regulatory, Ethical, and Trial Oversight Considerations

A1.1. REGULATORY AND ETHICAL CONSIDERATIONS

This trial will be conducted in accordance with the protocol and with the following:

- Consensus ethical principles derived from international guidelines including the Declaration of Helsinki and Council for International Organizations of Medical Sciences (CIOMS) international ethical guidelines
- Applicable ICH Good Clinical Practice (GCP) guidelines
- Applicable laws and regulations

The protocol, protocol amendments, ICF, IB and other relevant documents (e.g., advertisements) must be submitted to an IRB/IEC by the investigator and reviewed and approved by the IRB/IEC before the trial is initiated.

Any amendments to the protocol will require IRB/IEC approval before implementation of changes made to the trial design, except for changes necessary to eliminate an immediate hazard to trial participants.

Protocols and any substantial amendments to the protocol will require health authority approval prior to initiation except for changes necessary to eliminate an immediate hazard to trial participants.

The investigator will be responsible for the following:

- Providing written summaries of the status of the trial to the IRB/IEC annually or more frequently in accordance with the requirements, policies and procedures established by the IRB/IEC
- Notifying the IRB/IEC of SAEs or other significant safety findings as required by IRB/IEC procedures
- Providing oversight of the conduct of the trial at the site and adherence to requirements of 21 CFR, ICH guidelines, the IRB/IEC, European regulation 536/2014 for clinical studies (if applicable), and all other applicable local regulations

A1.2. FINANCIAL DISCLOSURE

Investigators and sub-investigators will provide the sponsor with sufficient, accurate financial information as requested to allow the sponsor to submit complete and accurate financial certification or disclosure statements to the appropriate regulatory authorities. Investigators are responsible for providing information on financial interests during the course of the trial and for 1 year after completion of the trial.

A1.3. INFORMED CONSENT PROCESS

The investigator or his representative will explain the nature of the trial, including the risks and benefits, to the participant and answer all questions regarding the trial.

Participants must be informed that their participation is voluntary. Participants will be required to

sign a statement of informed consent that meets the requirements of 21 CFR 50, local regulations, ICH guidelines, privacy and data protection requirements, where applicable, and the IRB/IEC or trial centre.

- The medical record must include a statement that written informed consent was obtained before the participant was enrolled in the trial and the date the written consent was obtained. The authorised person obtaining the informed consent must also sign the ICF.
- Participants must be reconsented to the most current version of the ICF(s) during their participation in the trial.
- A copy of the ICF(s) must be provided to the participant.

A participant who is rescreened is not required to sign another ICF if the rescreening occurs within 42 days from the previous ICF signature date, or there is a new ICF including updated safety or trial information.

A1.4. DATA PROTECTION

Participants will be assigned a unique identifier by the sponsor. Any participant records or datasets that are transferred to the sponsor will contain the identifier only; participant names or any information which would make the participant identifiable will not be transferred.

The participant must be informed that his personal trial-related data will be used by the sponsor in accordance with local data protection law. The level of disclosure must also be explained to the participant who will be required to give consent for their data to be used as described in the informed consent

The participant must be informed that his medical records may be examined by Clinical Quality Assurance auditors or other authorised personnel appointed by the sponsor, by appropriate IRB/IEC members, and by inspectors from regulatory authorities.

A1.5. SAFETY MONITORING COMMITTEE

Participant safety will be continuously monitored by the SMC.

The SMC, consisting of the sponsor trial physician, the Medical Monitor, a prostate cancer physician not participating in the trial, and at least 2 investigators will be appointed to review the trial data periodically or when needed and make recommendations concerning the continuation, modification or termination of the trial.

- The timings of SMC meetings will be defined in a trial-specific SMC Charter.
- The SMC will make recommendations about:
 - Opening each cohort in Phase 1
 - Choosing the regimen for Phase 2 and opening enrolment in Phase 2
 - Opening recruitment in Stage 2 of Phase 2, after reviewing available safety and efficacy data after at least 4 PSA responders have been identified
 - Altering the dose/ regimen (e.g., dropping back a dose level or dropping the second booster dose)
 - Pausing or stopping the trial
 - The institution of additional safety measures, if considered to be required

A1.6. DISSEMINATION OF CLINICAL TRIAL DATA

- Barinthus Biotherapeutics will share anonymised trial data on a publicly available database, as per local regulations.

Clinical Trial Reports (CSRs), periodic safety reports, and clinical trial summary reports will be disclosed after review by regulatory authorities. This includes access to Clinical Trial Reports from studies with negative outcomes and from terminated development programs.

A1.7. DATA QUALITY ASSURANCE

All participant data relating to the trial will be recorded on eCRFs unless transmitted to the sponsor or designee electronically (e.g., laboratory data). The investigator is responsible for verifying that data entries are accurate and correct by electronically signing the eCRF.

- Guidance on completion of eCRFs will be provided.

The investigator must permit trial-related monitoring, audits, IRB/IEC review, and regulatory agency inspections and provide direct access to source data documents.

Monitoring details describing strategy, including definition of trial critical data items and processes (e.g., risk-based initiatives in operations and quality such as risk management and mitigation strategies and analytical risk-based monitoring), methods, responsibilities, and requirements, including handling of noncompliance issues and monitoring techniques (central, remote or on-site monitoring) will be described in the monitoring plan.

The sponsor or designee is responsible for the data management of this trial, including quality checking of the data.

- The sponsor assumes accountability for actions delegated to other individuals (e.g., contract research organisations).

Records and documents, including signed ICFs, pertaining to the conduct of this trial must be retained by the investigator for 25 years after trial completion unless local regulations or institutional policies require a longer retention period. No records may be destroyed during the retention period without the written approval of the sponsor. No records may be transferred to another location or party without written notification to the sponsor.

A1.8. SOURCE DOCUMENTS

- Source documents provide evidence for the existence of the participant and substantiate the integrity of the data collected. Source documents are filed at the investigator's site.

Data entered in the eCRF that are transcribed from source documents must be consistent with the source documents or the discrepancies must be explained. The investigator may need to request previous medical records or transfer records, depending on the trial. Also, current medical records must be available.

Definition of what constitutes source data and its location will be agreed with the sites and documented.

The investigator must maintain accurate documentation (source data) that supports the information entered in the eCRF.

- Trial monitors will perform ongoing source data verification to confirm that data entered into the eCRF by authorised site personnel are accurate, complete and verifiable from source documents; that the safety and rights of participants are being

protected; and that the trial is being conducted in accordance with the currently approved protocol and any other trial agreements, ICH GCP and all applicable regulatory requirements.

A1.9. TRIAL AND SITE CLOSURE

The sponsor or designee reserves the right to close the trial site or terminate the trial at any time for any reason at the sole discretion of the sponsor. Trial sites will be closed upon trial completion. A trial site is considered closed when all required documents and trial supplies have been collected and a trial-site closure visit has been performed.

The investigator may initiate trial-site closure at any time, provided there is reasonable cause and sufficient notice is given in advance of the intended termination.

Reasons for the early closure of a trial site by the sponsor or investigator may include but are not limited to:

For trial termination:

- Discontinuation of further trial intervention development

For site termination:

Failure of the investigator to comply with the protocol, the requirements of the IRB/IEC or local health authorities, the sponsor's procedures or GCP guidelines

- Inadequate or no recruitment (evaluated after a reasonable amount of time) of participants by the investigator
- Total number of participants included earlier than expected

If the trial is prematurely terminated or suspended, the sponsor shall promptly inform the investigators, the IECs/IRBs, the regulatory authorities and any contract research organisation(s) used in the trial of the reason for termination or suspension, as specified by the applicable regulatory requirements. The investigator shall promptly inform the participant and should assure appropriate participant therapy and/or follow-up.

A1.10. PUBLICATION POLICY

The final trial report will be made available to the investigator for purposes of publications. The investigator and trial team must send all manuscripts, abstracts and presentations using data from this trial to the sponsor for review prior to their submission. The sponsor reserves the right to publish first or to delete any part or parts of the investigator's materials deemed to be confidential or proprietary.

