|--|--------------------------------------|----------------------------|----------------------|----------------------|---------------------|---------------------|-----------------------|---------------------|---------------------|----------------------------------|------------------------------------|----------------------------------|----------------------------------|---------------------|
| | | Day 1 Dosing Visit | Day 2 Telephone Call | Day 8 Telephone Call | Day 15 Clinic Visit | Day 29 Dosing Visit | Day 30 Telephone Call | Day 36 Clinic Visit | Day 43 Clinic Visit | Day 57 Dosing Visit ^b | Day 58 Telephone Call ^b | Day 64 Clinic Visit ^b | Day 71 Clinic Visit ^b | Day 91 Clinic Visit |
| Prior and concomitant medications | | <=====→ | | | | | | | | | | | | |
| Efficacy assessments | | | | | | | | | | | | | | |
| Serum PSA | X | X | | | | X | | | | X | | X | | X |
| Radiological assessment | X ⁱ | | | | | | | | | | | | | |
| Immunogenicity assessments | | | | | | | | | | | | | | |
| Blood for PBMC assessment ^j | | X | | | | X | | X | | X | | X | | X |
| Blood for ctDNA assessment | | X | | | | | | | | | | | | X |
| Blood for PSA-binding antibody/anti-vector antibody/anti-antigen antibody assessment | | X | | | X | X | | | X | X | | | X | X |

Abbreviations: AESI – Adverse Event of Special Interest, C3=Cohort 3, ChAd=ChAdOx1-PCAQ, CRP=C-reactive protein, CT=computed tomography, ctDNA=circulating tumour DNA, d=day(s), ECG=electrocardiogram, ECOG=Eastern Cooperative Oncology Group, MVA=MVA-PCAQ, MRI=magnetic resonance imaging, PBMC=peripheral blood mononuclear cells, PET=positron emission tomography, PSA=prostate-specific antigen, SAE=serious adverse event

^a If the screening period is longer than 42 days, the participant must be reconsented. Consult with the Medical Monitor for which assessments should be repeated.

^b Windows during the intervention period are calculated from the date of the previous VTP-850 dose.

^c If a cardiac event is reported, blood should be taken for an additional assessment of troponin T and the participant should undergo an additional ECG and echocardiogram at the earliest opportunity.

^d Historic echocardiogram may be used if performed within 3 months of Day 1.

^e May be retrieved at any time during the intervention period.

^f If troponin T test result is abnormal, a re-test on the following day is required.

^g Pre-dose and approximately 30 min post-dose.

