2.3.1 Risk Assessment

A summary of potential risks for VTP-850 administration is included in [Table 3](#).

Table 3 Summary of Potential Risks for VTP-850 Administration

| Potential Risk of Clinical Significance | Summary of Data/Rationale for Risk | Mitigation Strategy |
|--|---|---|
| Trial Intervention (VTP-850) | | |
| A potential signal of cardiac risk has been identified and assessed following administration of VTP-850 in the trial population | In the first 14 participants treated, a potential cardiac-related death has been reported together with non-serious adverse events of dyspnoea, and dyspnoea exertional and atrial fibrillation in two further participants. These events have a possible temporal relationship to trial intervention, occurring within a similar timeframe after the first MVA-PCAQ boost. | Participants with a history of cardiac events that put them at risk will be excluded from the trial. In addition, cardiac monitoring (ECG and laboratory blood tests) will be performed at pre-defined timepoints during the first 6 months of the trial and a baseline echocardiogram will be performed to exclude participants with any clinically significant abnormalities. |
| Potential for local reactions (injection site redness, injection site swelling and injection site pain) and systemic reactions (including fever, chills, feverishness and headache) following IM administration. | These are common reactions seen with other products that use the same viral vectors as are used in VTP-850. Further details are provided in the current IB. | The investigator site will contact the participant one day after the administration of each component of VTP-850 7 days after the administration of ChAdOx1-PCAQ, and the participant will return to the clinic 7 days after each administration of MVA-PCAQ, at which times the trial staff will record AEs |
| With any immunotherapeutic there is a rare risk of anaphylaxis which can be fatal. | - | Participants will be dosed in a clinical area where appropriate drugs and medical equipment to treat acute anaphylactic reactions are immediately available for the management of such adverse reactions in the immediate post-administration period. Participants are observed in the clinic for at least 30 min post-dose. Participants with history of anaphylaxis to previous vaccination are excluded. |

| Potential Risk of Clinical Significance | Summary of Data/Rationale for Risk | Mitigation Strategy |
|---|--|---|

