5.3 Screen Failures

A screen failure occurs when a participant who consents to participate in the clinical trial is not subsequently entered in the trial. A minimal set of screen failure information is required to ensure transparent reporting of screen failure participants to meet the Consolidated Standards of Reporting Trials (CONSORT) publishing requirements and to respond to queries from regulatory authorities. Minimal information includes demography, screen failure details, eligibility criteria, and any SAE causally related to a screening procedure.

Individuals who do not meet the criteria for participation in this trial (screen failure) may be rescreened after discussion with the medical monitor.

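### The rescreening sentence in Protocol Appendix 1, A1.3 is inverted: it makes an updated consent form a ground for not signing again

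*Protocol*

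**What the plan says.** Protocol Section 5.3 allows rescreening: people who fail screening "may be rescreened after discussion with the medical monitor". Consent for these men is governed by one sentence in Appendix 1, A1.3. A rescreened participant "is not required to sign another ICF if the rescreening occurs within 42 days from the previous ICF signature date", and the sentence then adds a second condition, "or there is a new ICF including updated safety or trial information".

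Two other provisions bear on the same situation:

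- A general bullet in A1.3: "Participants must be reconsented to the most current version of the ICF(s) during their participation in the trial".
- Footnote a to Table 1 in Section 1.3: "If the screening period is longer than 42 days, the participant must be reconsented". Section 4.1.4 defines the Screening Period as running for up to 42 days, from informed consent to the prime dose.

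Risk information did change while the trial was running. Section 2.3.1 reports: "In the first 14 participants treated, a potential cardiac-related death has been reported".

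**The concern.** Both conditions in the rescreening sentence depend on the same *if*, so each one alone excuses the man from signing. A revised ICF with new safety content would normally be the reason to ask for a fresh signature. Here it is written as a reason not to. A site looking up what to do with a rescreened man will find this sentence first, because it is the only one about rescreening. It gives the opposite answer to the general rule in the same section.

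What is at stake is documented consent to current risk information in a first-in-human trial with a possible cardiac signal. The matter is still live. The SAP (Section 2.1) says Phase 2 has not commenced, and the Protocol plans 19 participants in Stage 1 and up to 100 more in Stage 2, at up to 30 centres.

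**Working it through.** There is no figure to reproduce, so the check is logical. Let A be *rescreened within 42 days of the previous signature* and B be *a new ICF with updated safety or trial information exists*. The sentence waives the signature if A or B holds. With *unless* in place of *or*, it would waive the signature only if A holds and B does not.

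| Case | A: within 42 days | B: new ICF | As written | With *unless* |
|---|---|---|---|---|
| 1 | yes | no | waived | waived |
| 2 | yes | yes | waived | signature required |
| 3 | no | no | not waived | signature required |
| 4 | no | yes | waived | signature required |

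As written, the signature is waived in both cases where an updated form exists (2 and 4). The only case left without a waiver is case 3, in which there is nothing new to disclose. Changing the one word corrects cases 2 and 4 and leaves 1 and 3 as they are.

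The next step is to set the other provisions against cases 2 and 4.

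*Footnote a with Section 4.1.4.* If a rescreened man does not sign again, his earlier consent is the only date from which his Screening Period can be counted. If he has not been dosed 42 days after that date, his screening has exceeded 42 days and footnote a requires reconsent. This covers case 4 in substance, and any man in case 2 whose first dose falls after day 42. It is an inference, because the footnote addresses a long screening period and does not mention rescreening.

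*The general bullet in A1.3.* It requires reconsent to the current version, which is the reverse of the rescreening sentence in cases 2 and 4. It sets the time only as during participation, and does not place reconsent before rescreening procedures or before first dose.

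*Other checks.* A1.3 also requires written consent to be recorded before enrolment, but does not say which version. Table 1 marks informed consent at Screening only. The Day 1 pre-dose check is of eligibility, with no stated check of the ICF version.

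The case left without a clear safeguard is therefore narrow. First consent, screen failure, release of a new ICF and rescreening all fall within 42 days. If first dose also falls inside that window, only the untimed general bullet applies.

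That sequence is possible. Protocol Versions 4.0 and 5.0, both changed to address cardiac risk, are dated 04 March 2024 and 18 April 2024: 27 days left in March plus 18 in April is 45 days. The ICFs and their dates are not in the documents, so it is an assumption that consent forms were revised on a similar timetable.

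**The case against.** The strongest reply is that the Protocol taken as a whole does not permit what the sentence seems to permit. The general bullet is mandatory. It is hard to argue that it misses rescreened men on the ground that they were never entered: Section 5.3 and A1.3 both call such men participants, the SAP's All Screened Set counts every participant who signed a consent form, and a man about to be dosed has been entered by then. Footnote a catches most delayed cases. A1.3 also requires the investigator or a representative to explain the risks, and requires consent to meet 21 CFR 50, ICH and IRB/IEC requirements. A1.8 has monitors verify that participants' rights are protected. On this view *or* is a slip that any trained site would read correctly.

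Most of that stands. A reader might infer from the sentence that men can be rescreened and dosed on outdated risk information, or that every rescreened man with a newer ICF will be mishandled. The documents do not support either reading. The sentence concerns a signature and does not remove the duty to explain risks, and the other provisions still apply alongside it. Nor is the waiver confined to men with a new ICF, since case 1 is waived as well.

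The reply does not remove the contradiction. A specific rule and a general rule in one section give opposite answers, and neither the general bullet nor footnote a says that the current form must be signed before rescreening procedures begin.

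**Conclusion.** The point holds as an internal contradiction in an operative consent rule of the current Protocol (Version 5.0). The rescreening sentence is inverted, conflicts with the reconsent bullet in its own section, and fits poorly with Table 1 footnote a. A site that follows the specific sentence could rescreen a man within 42 days without his signing an updated ICF. Dosing him on superseded consent is possible if dosing also falls within that window, but it does not follow from the Protocol read as a whole.

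The number of men affected cannot be derived: the documents give neither the rescreening count nor the ICF revision dates. The cardiac signal is a reason to correct the sentence, and is not evidence that anyone was consented wrongly. The conclusion rests on the literal reading of *if … or*, and on counting a rescreened man's screening period from his earlier consent when he has not signed again. No endpoint, analysis set, sample size or estimate changes.

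**What to change.** In A1.3, replace *or there is a new ICF* with *unless there is a new ICF*. Add a timing clause stating that the current ICF version must be signed before any rescreening procedure and before first dose. Align this with the reconsent bullet and footnote a, so that all three give the same answer for a rescreened man.

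The cost is one word and one clause. Protocol amendments need IRB/IEC approval under A1.1, so the correction is best carried in the next planned amendment. It requires no change to the SAP.

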12.2 Appendix 2: Clinical Laboratory Tests – Analytes and Laboratory Locations

- The tests detailed in [Table 7](#) will be performed by the central laboratory with the exception of troponin T which will be performed by local laboratories.

Except for troponin T, local laboratory results are only required if the central laboratory results are not available in time for either trial intervention administration and/or response evaluation. If a local sample is required, it is important that the sample for central analysis is obtained at the same time. Additionally, if the local laboratory results are used to make either a trial intervention decision or response evaluation, the results must be recorded.

- Protocol-specific requirements for inclusion or exclusion of participants are detailed in Section 5 of the protocol.

Additional tests may be performed at any time during the trial as determined necessary by the investigator or required by local regulations.

Table 7 Protocol-Required Laboratory Safety Tests

| Laboratory Tests | Parameters | | | |
|--|--|---|--|--|
| Haematology | Platelet count Red blood cell (RBC) count Haemoglobin Haematocrit | RBC indices: Mean corpuscular volume (MCV) Mean corpuscular haemoglobin (MCH) %Reticulocytes | White blood cell (WBC) count with differential: Neutrophils Lymphocytes Monocytes Eosinophils Basophils | |
| Biochemistry | Blood urea nitrogen (BUN) Calcium Creatinine Glucose (non-fasting) Potassium Sodium Total protein | | | |
| Liver function tests | Alanine aminotransferase (ALT) Alkaline phosphatase (ALP) Aspartate aminotransferase (AST) Total and direct bilirubin | | | |
| Markers for cardiac dysfunction or inflammatory response | Troponin T C-reactive protein (CRP) | | | |
| Routine urinalysis | 
 Specific gravity pH, glucose, protein, blood, ketones, bilirubin, urobilinogen, nitrite, leukocyte esterase by dipstick (read locally) Microscopic examination (if blood or protein is abnormal) | | | |

Investigators must document their review of each laboratory safety report.

12.3 Appendix 3: AEs, AESIs and SAEs: Definitions and Procedures for Recording, Evaluating, Follow-up and Reporting

A3.1. DEFINITION OF AE

AE Definition

- An AE is any untoward medical occurrence in a participant or clinical investigation subject administered the investigational product and which does not necessarily have to have a causal relationship with this treatment.
- An AE can therefore be any unfavourable and unintended sign (including an abnormal laboratory finding), symptom or disease temporally associated with the use of trial intervention, whether considered related to the investigational product.

Events Meeting the AE Definition

- Any clinically significant worsening of a pre-existing condition
- An AE occurring from overdose of an investigational or marketed product, whether accidental or intentional
- An AE occurring from abuse (e.g., use for non-clinical reasons) of an investigational or marketed product

An event related to a medical procedure or associated with the discontinuation of the previous use of an investigational or marketed product required by protocol (protocol related AE)

- Not all vital sign or laboratory abnormalities will be considered an AE. Usually these will be considered as an AE:
 - If CTCAE Grade 3 (severe) or greater in severity
 - If judged to be clinically significant by the investigator
 - If accompanied by clinical symptoms
 - If meeting the definition of an SAE
 - If resulting in dose interruption or discontinuation of trial intervention
 - If requiring specific treatment

Events NOT Meeting the AE Definition

- Any clinically significant abnormal laboratory findings or other abnormal safety assessments that are associated with the underlying disease, unless judged by the investigator to be more severe than expected for the participant's condition
- The disease/disorder being studied (prostate cancer) or expected progression, signs, or symptoms of the disease/disorder being studied, unless more severe than expected for the participant's condition
- Medical or surgical procedure (e.g., endoscopy, appendectomy): the condition that

leads to the procedure is the AE

- Situations in which an untoward medical occurrence did not occur (social and/or convenience admission to a hospital)
- Anticipated day-to-day fluctuations of pre-existing disease(s) or condition(s) present or detected at the start of the trial that do not worsen

Recording Medical Occurrences Prior to Trial Dosing

- Any medical occurrence that occurs after the participant has given their informed consent and prior to the start of the first dose of VTP-850, including clinically significant abnormalities found in screening assessments, will be considered part of the participant's medical history.

A3.2. DEFINITION OF AESI

AESI Definition

An AESI is defined as:

- any cardiac event
- shortness of breath / dyspnoea
- abnormal cardiac investigation or examination

A3.3. DEFINITION OF SAE

An SAE is defined as any untoward medical occurrence that meets one of more of the criteria listed that occurs after the start of the first dose of VTP-850, or occurs after informed consent has been provided and is causally related to a trial procedure:

Results in death (i.e., the adverse event caused or led to the fatality). Serious does not describe an event which hypothetically might have caused death if it were more severe

a. Is life threatening

The term *life threatening* in the definition of *serious* refers to an event in which the participant was at risk of death at the time of the event. It does not refer to an event, which hypothetically might have caused death, if it were more severe.

b. Requires inpatient hospitalisation or prolongation of existing hospitalisation

It required inpatient hospitalisation or prolonged hospitalisation beyond the expected length of stay. Hospitalisations for scheduled treatments and elective medical/surgical procedures related to a pre-existing condition that did not increase in severity or frequency following receipt of trial intervention, are not serious by this criterion. Hospitalisation is defined as a hospital admission or an emergency room visit for a period greater than 24 h

- Hospitalisation for social reasons or for elective treatment of a pre-existing condition that did not worsen from baseline is not considered an AE.

c. Results in persistent or significant disability/incapacity

- The term disability means a substantial disruption of a person's ability to conduct normal life functions.

This definition is not intended to include experiences of relatively minor medical significance such as uncomplicated headache, nausea, vomiting, diarrhoea, influenza, and accidental trauma (e.g., sprained ankle) that may interfere with or prevent everyday life functions but do not constitute a substantial disruption.

d. Is a congenital anomaly/birth defect (i.e., an adverse finding in a child or foetus of a participant exposed to the trial intervention prior to conception or during pregnancy).

Other medically significant events:

- An adverse finding that may not result in death, threaten life or require hospitalisation (i.e., the adverse event does not meet any of the above serious criteria) may be considered an SAE when, based on appropriate medical judgment, they may jeopardise the participant and require medical or surgical intervention to prevent one of the serious outcomes listed in these criteria (e.g., allergic bronchospasm requiring intensive treatment in an emergency room or at home, blood dyscrasias or convulsions that do not result in hospitalisation, or the development of drug dependency or drug abuse).

A3.4. RECORDING AND FOLLOW-UP OF AE AND/OR SAE

AE and SAE Recording

- All AEs are recorded in the eCRF at all telephone and clinic visits until the Month 6 visit. All AEs will be reported using a recognised medical term or diagnosis that accurately reflects the event.
- Adverse events will be assessed by the investigator, or a medically qualified trial team member, for severity, relationship to VTP-850, action taken, outcome and whether the event meets criteria as an SAE according to the guidelines in this appendix.

Assessment of Intensity

- The severity of AEs and laboratory values will be graded according to the Common Terminology Criteria for Adverse Events (CTCAE) Version 5.0. The scale shown in [Table 8](#) will be used to assess severity of AEs not listed in the CTCAE.

Table 8 Severity Grading of Adverse Events not listed in CTCAE

| Grade | Severity ¹ | |
|-------|-----------------------|---|
| 1 | Mild | Asymptomatic or mild symptoms; clinical or diagnostic observations only; or intervention not indicated. |

| | | |
|---|-----------------|--|
| 2 | Moderate | Minimal, local or non-invasive intervention indicated; limiting age-appropriate instrumental Activities of Daily Living (ADL) ² . |
| 3 | Severe | Severe or medically significant but not immediately life-threatening; hospitalisation or prolongation of hospitalisation indicated; disabling; limiting self care ADL ³ . |
| 4 | Lifethreatening | Life-threatening consequences; urgent intervention indicated. |
| 5 | Fatal | Death related to this AE |

¹ A semi-colon indicates 'or' within the description of the grade

² Instrumental ADL refer to preparing meals, shopping for groceries or clothes, using the telephone, managing money, etc.

³ Self care ADL refer to bathing, dressing and undressing, feeding self, using the toilet, taking medications and not bedridden.

A change in severity of an AE will be recorded as a new AE with the outcome of the event prior to the change in severity stated as "change in severity". The onset and resolution dates will encompass the duration of each severity.

Note: It is important to distinguish between serious and severe AEs. Severity is a measure of intensity whereas seriousness is defined by the criteria in [Section A3.3](#).

Assessment of Causality

For all AEs reported in the eCRF, the investigator will determine a **causal relationship** to VTP-850.

A number of factors will be considered in making this assessment, including: 1) the temporal relationship of the event to the administration of VTP-850, 2) whether an alternative aetiology has been identified and 3) biological plausibility.

Causality of all adverse events should be assessed by the investigator using the following question:

"Is there a reasonable possibility that the adverse event may have been caused by VTP-850?"

- **YES (related):** There is a reasonable possibility that VTP-850 contributed to the AE
- **NO (not related):** There is no reasonable possibility that the AE is causally related to the administration of VTP-850. There are other, more likely causes and administration of VTP-850 is not suspected to have contributed to the AE

The investigator is required to provide an assessment of relationship of AEs to VTP-850 or trial procedures and determine causality. The sponsor and Medical Monitor can add another causality assessment to the investigator's causality. If the sponsor or the Medical Monitor disagrees with the investigator's causality assessment, the opinion of both the investigator, the sponsor and the Medical Monitor should be provided with the report.

Every effort should be made by the investigator to determine the existence of any pre-existing conditions (e.g., headache on trial Day 1 with onset prior to VTP-850 administration) that must be taken into consideration when assessing causal relationship of an AE. Pre-existing conditions should be recorded in the eCRF as medical history and substantiated by appropriate source documentation. Intermittent conditions such as headaches may be present on trial Day 1 but may

represent an AE if the intensity or duration of the event is worse than usual following trial intervention.

Assessment of Outcome

The outcome of the AE will be assessed as:

- Recovered/resolved
- Recovered/resolved with sequelae
- Not recovered/resolved
- Unknown
- Fatal
- Change in severity

Follow-up of AEs and SAEs

Treatment of any AEs will be determined by the investigator using their best medical judgment and according to current clinical practice guidelines. All applied measures as well as follow-up will be recorded in the appropriate eCRF.

The investigator will continue follow-up on AEs, including laboratory abnormalities, until the event has resolved, stabilised, is otherwise explained, the participant completes the trial or is lost to follow-up. The resolution date will be recorded on the eCRF as the last date on which the participant experienced the AE. If an AE resolution date is uncertain the investigator should estimate the completion date based on medical judgment and interview of the participant. Approximate dates of resolution from phone or other communications may be taken as AE resolution dates. Some examples of estimation of adverse event resolution are: 1) an asymptomatic laboratory abnormality on one visit that has not been followed up between visits but has resolved by the next visit may be assumed to have resolved by the midpoint of the inter-visit interval; 2) A resolved AE that was treated may be assumed to have been resolved by the end of treatment.

Adverse events that are still present at the end of the trial should be recorded as ongoing.

Information recorded on the eCRF must be substantiated in the source documents. If an AE evolves into a condition that becomes “serious,” it will be designated as serious on the AE eCRF, and a supplemental SAE report form will be completed.

Follow-up for SAEs will be attempted until resolution or stabilisation and the outcome reported to the sponsor, even if this extends beyond the SAE reporting period.

A3.5. REPORTING OF SAEs AND/OR AESIs

All SAEs/AESIs are reported to the sponsor or designee until the end of the trial. Suspected unexpected serious adverse reactions are reported even after the trial is over, if the investigator becomes aware of them. The trial centre will be provided with specific reporting procedures including the SAE/AESI Report form and any supplemental reporting forms to be used.

SAEs/AESIs will be reported on the SAE/AESI form and the AE eCRF using a recognised medical term or diagnosis that accurately reflects the event.

